3.7.6 Clinical Laboratory Parameters

Laboratory parameters (collected for Japanese subjects only) will be summarized at each visit by treatment group. Frequencies of worst observed Grade 3-4 toxicity, as defined by the Division of AIDS (DAIDS) Table for Grading the Severity of Adult and Pediatric Adverse Events (available at https://rsc.niaid.nih.gov/clinical-research-sites/daids-adverse-event-grading-tables), will be presented for each laboratory parameter below by treatment group:

- CBC: hemoglobin, platelets
- WBC with differential: white blood cell count
- Liver function: bilirubin, AST/ALT
- Chemistry general: creatinine.

Also, laboratory parameters will be assessed by presenting tables containing information associated with 2-grade (or greater) laboratory shifts from baseline. All other serum chemistry and hematology parameters not listed above will be presented in the data listings.

For laboratory values reported as lower than the lower limit of quantification (LLOQ), a value equal to half of the limit of quantification will be imputed in the summaries. However, < LLOQ will be reported in the listings.

3.7.7 Other Safety Evaluations

Additional data collected throughout the study include screen failure data, significant findings in medical history and physical exam, vital signs, and concomitant medications through Day 361. Data listings will be provided for these data. In addition, the vaccines given to the subjects throughout the study will be summarized by treatment group.

Upon review of the listings, additional summary tables may be generated as appropriate.

3.8 Anti-drug Antibodies

For each season as well as the two consecutive seasons (ie, Season 1, Season 2, Season 1 + Season 2) the summaries will be provided using the respective as-treated population. For Season 1, summaries of ADA to palivizumab and MEDI8897 will be provided for palivizumab and MEDI8897 group, respectively. The Season 1 summaries will also be provided for each cohort (pre-term, CHD/CLD). For Season 2, summaries of ADA to MEDI8897 will be provided for Palivizumab/MEDI8897 group only. For Season 1 + Season 2, summaries of ADA to palivizumab and MEDI8897 will be provided for

palivizumab/palivizumab and MEDI8897/MEDI8897 group, respectively. There is no intention to compare results of ADA to MEDI8897 and ADA to palivizumab.

The number and percentage of subjects who develop anti-MEDI8897 antibodies will be summarized at each visit by treatment group. For those with a positive assessment, the ADA titer results will also be summarized. The number and percentage of ADA positive samples with specificity to the YTE or RSV-neutralizing regions of MEDI8897 will also be summarized.

An additional table will summarize the number and percentage of subjects positive for ADA at baseline and positive at any post-baseline time point. The percentage who were persistent positive and transient positive will also be presented.

- Persistent positive is defined as negative at baseline and positive at ≥ 2 post-baseline assessments (with ≥ 16 weeks between first and last positive) or positive at last post-baseline assessment
- 2 Transient positive is defined as negative at baseline and at the last post-baseline assessment, and positive at ≥ 1 post-baseline assessment and not fulfilling the conditions for persistent positive.

To evaluate the impact of ADA on efficacy and safety, the efficacy endpoints (ie, incidence of medically attended RSV LRTI and RSV hospitalization), as well as TEAE and SAE by SOC and PT based on MedDRA will be summarized by ADA post-baseline status (ie, at least one post-baseline ADA positive or not through 360 days post 1st dose). The efficacy endpoints will also be summarized by ADA post-baseline status through 150 days post 1st dose.

The impact of ADA on PK will be evaluated as described in Section 3.9

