Overall, the incidence of investigational product-related TEAEs (MEDI8897 2.3%, placebo 2.1%); adverse events of special interest (AESIs), including hypersensitivity, immune complex disease, and thrombocytopenia (MEDI8897 0.5%, placebo 0.6%); and new onset chronic diseases [REDACTED] was low and generally comparable between the placebo and MEDI8897 groups. AESIs were reported in 5 subjects (4 subjects with rash or rash macular and 1 subject with petechiae) in the MEDI8897 group and 3 subjects (rash or rash papular) in the placebo group. All events were Grade 1 in severity. The TEAE of petechiae that was reported as an AESI was 1-day duration and was reported by the site investigator based on description by the parent. There were no laboratory assessments for the petechiae.

TEAEs that involved the skin and subcutaneous tissues (including diaper rash) were collected as skin reactions, with a few exceptions for skin reactions that could be definitively diagnosed such as impetigo, varicella, and scabies. [REDACTED]

Following a single fixed 50-mg IM dose of MEDI8897, over 95% of measurable Day 151 concentrations were greater than the nonclinical EC₉₀ target of 6.8 µg/mL. The median area under the concentration-time curve from time 0 to infinity (AUC_{0-∞}) and estimated apparent t_{1/2} were 5.3 day.mg/mL (range, 3.2 to 10.2 day.mg/mL) and 56.5 days (range, 46.8 to 81.1 days), respectively.

Overall, the rate and titers of ADA were low, and in ADA-positive subjects there was no effect on PK or safety. Of the subjects who had serum samples available for testing, ADA was detected post baseline in 4.3% (40/921) of subjects in the MEDI8897 group and 2.8% (13/466) of subjects in the placebo group; with less than 5% of subjects in either group being ADA positive at any visit. ADA titers ranged from 1:50 to 1:3,200 in the MEDI8897 group and 1:50 to 1:200 in the placebo group. Of the MEDI8897 subjects who were post-baseline ADA positive, ADA targeting the YTE domain was observed in 4/17 subjects on Day 151 and 10/15 on Day 361. Two MEDI8897 subjects had ADA on Day 361.

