The endpoints to be measured in this study are described in Section 2.

Figure 1 Study Flow Diagram

ADA = anti-drug antibody; CHD = congenital heart disease; CLD = chronic lung disease; IM = intramuscular; PK = pharmacokinetic.

SEASON 1: Randomization for Season 1 Day 1, 2:1 MEDI8897 or palivizumab group

SEASON 2 (CLD/CHD cohort only): Randomization for Season 2 Day 1: Subjects who were randomized in Season 1 to receive MEDI8897 will receive MEDI8897 in Season 2.

Subjects who were randomized to receive palivizumab in Season 1 will receive MEDI8897 or palivizumab in Season 2

Blood samples for PK and ADA: Season 1 for both cohorts – Screening or Day 1 predose and on Days 31 (predose), 151, and 361 (for CLD/CHD cohort, prior to Season 2 dosing); Season 2 for CLD/CHD cohort only - Days 31 (predose), 151, and 361. Additionally, samples will be collected during both seasons from all subjects hospitalized for a respiratory infection, and before and after cardiac surgery with cardiopulmonary bypass for subjects with CHD requiring a replacement dose of study drug.

Safety assessments will be performed through Day 361 for each respective season.

^a In the MEDI8897 group Season 1, dose level will be stratified by body weight at time of dosing; subjects will receive 50 mg MEDI8897 if < 5 kg or 100 mg MEDI8897 if ≥ 5 kg.

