4.8.5.2 Anti-drug Antibody Analysis

The incidence of ADA to MEDI8897 and to palivizumab will be assessed and summarized by number and percentage of subjects who are ADA positive by treatment group. The impact of ADA on PK, and association with TEAEs and TESAEs, will be assessed.

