3.7.1 Adverse Events and Serious Adverse Events

Adverse events and serious adverse events will be coded by MedDRA version 22 or higher and the type, incidence, severity and relationship to study investigational product will be summarized by treatment group. Specific AEs will be counted once for each subject for calculating percentages. In addition, the total number of AEs will also be provided. In addition, if the same AE occurs multiple times within a particular subject, the highest severity and level of relationship observed will be reported. All treatment-emergent AEs (TEAEs) and treatment-emergent SAEs (TESAEs) occurring through Day 361 will be summarized overall, as well as categorized by MedDRA SOC and PT. In addition, the TEAEs occurring at 1% or higher in either treatment group will be reported by PT.

Nontreatment-emergent AEs/serious adverse events (SAEs), defined as AEs/SAEs that occur prior to the administration of investigational product, or after Day 361, Season 1 for preterm cohort, or after Day 361, Season 1 and prior to Day 1, Season 2 for CHD/CLD cohort, or after Day 361, Season 2 for CHD/CLD cohort, or pre-planned surgeries that are coded with PT "Cardiac Operation" and occur during the study for CHD subjects will be presented in the listings.

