3.9 Pharmacokinetics

Individual MEDI8897 and palivizumab serum concentrations for each nominal sampling time will be listed and summary descriptive statistics presented by treatment group and cohort (preterm, CHD/CLD) in Season 1, and by treatment group in Season 2, respectively. Geometric mean MEDI8897 serum concentrations will be plotted versus time. Individual MEDI8897 serum concentrations will be graphically illustrated, and summarized, by ADA status.

Further, model-based evaluation of PK, and efficacy extrapolation, will be detailed in a separate PK extrapolation plan and reported outside the CSR.

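### The ADA-impact tables in SAP 3.8 do not order events against ADA dates, so events before the first positive sample count as events in ADA-positive infants

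*SAP*

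**What the plan says.** SAP 3.8 gives the purpose of these tables as evaluating the impact of ADA on efficacy and safety. The efficacy endpoints, RSV LRTI and RSV hospitalization, "as well as TEAE and SAE by SOC and PT based on MedDRA will be summarized by ADA post-baseline status". Each infant is classed once: all these outcomes are "summarized by ADA post-baseline status (ie, at least one post-baseline ADA positive or not through 360 days post 1st dose". A further sentence covers efficacy only: "The efficacy endpoints will also be summarized by ADA post-baseline status through 150 days post 1st dose". The safety tables have no such version.

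Protocol 3.1.1 (Figure 1 notes) schedules Season 1 ADA samples at "Screening or Day 1 predose and on Days 31 (predose), 151, and 361", with an additional sample for every infant hospitalized for a respiratory infection. SAP Appendix 2 gives the EU no Day 31 window, so the only scheduled in-season sample there is Day 151.

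On safety, Protocol 4.8.5.2 promises that the "association with TEAEs and TESAEs, will be assessed", whereas SAP 3.8 names TEAE and SAE. SAP 3.7.1 confines "AEs/SAEs that occur prior to the administration of investigational product", along with planned cardiac operations, to listings.

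On PK, SAP 3.9 says: "Individual MEDI8897 serum concentrations will be graphically illustrated, and summarized, by ADA status". It does not define that status.

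**The concern.** An event that precedes ADA cannot have been caused by it. An infant with an RSV LRTI on Day 60 and a first positive sample on Day 361 would still be tabulated as an RSV LRTI with ADA. Nothing in SAP 3.7 to 3.9 prevents this. For infants first positive at Day 361, every 150-day efficacy event precedes the positive sample, and so does nearly every TEAE. Counting such events usually pulls the two rows together, so a table meant to detect harm from ADA is less able to show it. Safety is the primary objective, and the safety tables are the ones with no shorter-window version.

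Two smaller points go with this. Read literally, SAE in SAP 3.8 lets in pre-dose events and planned operations that SAP 3.7.1 keeps out of summaries. And if SAP 3.9 uses whole-period status, the Day 31 and Day 151 concentrations of an infant first positive at Day 361 are summarized as ADA-positive levels.

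**Working it through.** **Plan's own figures.** 600 × 0.06 = 36 RSV LRTI events on MEDI8897, as in SAP 2.4. 40/921 = 4.34%, as in the Phase 2b summary in Protocol 1.4.1. At that rate 600 × 0.0434 = 26 infants would be ADA positive, with 26 × 0.06 = 1.6 RSV LRTI events. SAP 2.4 warns that rates could be much lower; at an assumed 1% to 2% the figure is 0.3 to 0.5.

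**Timing of first positives (assumed).** The documents do not give it. Protocol 1.4.1 reports that "ADA targeting the YTE domain was observed in 4/17 subjects on Day 151 and 10/15 on Day 361". If 17 and 15 are all the positives at those visits and do not overlap, the shares of the 40 positives are 17/40 = 42.5% at Day 151 and 15/40 = 37.5% at Day 361. The remaining 8/40 = 20% is placed at Day 31. On the EU schedule that 20% moves to Day 151, giving 62.5% and 37.5%.

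**Formula.** Assume a constant event rate that is three times higher after ADA onset. Ratio shown = 1 + (3 − 1) × S, where S is the weighted share of the event window after onset. Onset is put either at the sample (30, 150, 360 days after Dose 1) or midway between samples (15, 90, 255 days; EU 75 and 255).

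| Table | S, onset at sample | Ratio | S, midpoint onset | Ratio |
|---|---|---|---|---|
| TEAEs, 360 days | 0.20×330/360 + 0.425×210/360 = 0.431 | 1.86 | 0.20×345/360 + 0.425×270/360 + 0.375×105/360 = 0.620 | 2.24 |
| RSV LRTI, 150 days, by 360-day status | 0.20×120/150 = 0.16 | 1.32 | 0.20×135/150 + 0.425×60/150 = 0.35 | 1.70 |
| RSV LRTI, 150 days, by 150-day status | 0.16/0.625 = 0.256 | 1.51 | 0.35/0.625 = 0.56 | 2.12 |
| EU: TEAEs, 360 days | 0.625×210/360 = 0.365 | 1.73 | 0.625×285/360 + 0.375×105/360 = 0.604 | 2.21 |
| EU: RSV LRTI, by 360-day status | 0 | 1.00 | 0.625×75/150 = 0.3125 | 1.63 |
| EU: RSV LRTI, by 150-day status | 0 | 1.00 | 0.3125/0.625 = 0.50 | 2.00 |

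The 150-day-status rows drop the 37.5% first positive at Day 361 and assume that the Day 151 sample counts.

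**Check with a second model.** Take a 6% risk over 150 days, so H = −ln(0.94). The risk with onset on day T is 1 − exp{−H[T/150 + HR × (150 − T)/150]}. Spread onset evenly from Day 15 to the end of the 150 days, with 0%, 37.5% or 50% of positives having onset after Day 150. A true hazard ratio of 3 then shows as a risk ratio of 1.85, 1.53 or 1.42. A true 2 shows as 1.43, 1.27 or 1.22. With no ADA effect at all, 55%, 72% or 78% of RSV LRTIs in ADA-positive infants precede onset.

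**Bias the other way.** Let p = 40/921. Suppose a hospitalization sample adds an independent chance e × 17/921 of a positive result, with e assumed between 0.25 and 1. Then q = 1 − (1 − p)(1 − e × 17/921) = 0.048 to 0.061. The apparent hospitalization ratio is (q/p) ÷ [(1 − q)/(1 − p)] = 1.11 to 1.43 with no true effect.

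**The case against.** The best reply is that the plan already reduces the problem and that other limits dominate. Efficacy is also tabulated by ADA status through 150 days, which, read as a 150-day status, removes infants first positive at Day 361. That stands as a partial remedy. It sets no order within the 150 days, helps least where Day 151 is the only scheduled in-season sample, and does nothing for safety.

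The study is descriptive and ADA-positive events will be few. Even with perfect ordering, 26 against 574 infants at 12% against 6% gives about 29% power (normal approximation). That stands too, but with so few events a single misplaced case changes the row, which favors a dated listing.

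The size is soft. The timing shares come from denominators for YTE-specific ADA, and no Day 31 result is reported. The formula gives a rate ratio, whereas SAP 3.7.1 counts an infant once per AE, so an any-TEAE percentage could reach a ceiling. A positive sample also dates onset only to an interval: some events before the sample may have followed true onset.

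A reader might infer that the tables hide any real ADA effect, or would look reassuring whatever the truth. The figures do not support that. Most scenarios show a reduced but visible ratio, and 1.00 arises only on the EU schedule with onset on the sample date itself, which is implausible. Nor is the direction fixed: hospitalization-triggered samples can inflate the ratio, and infants who withdraw early have fewer samples and tend to be classed negative.

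A reader might also want a landmark analysis as the main table. At Day 31 that would rest on about 26 × 0.20 = 5 infants and 5.2 × 0.06 × 120/150 = 0.25 RSV LRTI events, and infants who turn positive after the landmark would count as negative.

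Finally, SAE may be shorthand for TESAE, and SAP 3.9 does not say that it uses whole-period status. Both need clarifying; neither is a demonstrated error.

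**Conclusion.** The point holds as a bias, not as a fatal flaw. SAP 3.8 uses whole-period ever/never status and does not order dates, so events before the first positive sample count in the ADA-positive row. The comparison is usually pulled toward no difference, with a possible opposite pull for RSV hospitalization. A true threefold post-onset rate would appear as about 1.9 to 2.2 for 360-day TEAEs. For 150-day RSV LRTI it would appear as 1.3 to 1.7 by 360-day status and 1.5 to 2.1 by 150-day status. On the EU schedule the figures are 1.7 to 2.2, 1.0 to 1.6 and 1.0 to 2.0. These ranges rest on the assumed 20%/42.5%/37.5% timing, a constant event rate and the two onset conventions. The change is worth making because it is cheap and removes a known misclassification relative to the first positive sample; it does not cure sparse data.

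**What to change.** - Keep the existing ADA tables. Add one supporting table and one dated listing that split events in ADA-positive infants into before versus on or after the first positive sample. Show event day and sample day, and flag hospitalization-triggered samples.
- State in SAP 3.8 whether the 150 days in the extra efficacy summary apply to the endpoint, to ADA status or to both, and whether triggered samples count toward status.
- Optionally add a Day 151 landmark as support: ADA status at or before Day 151 against events from Day 152 to Day 361, among infants still in the study.
- Replace SAE with TESAE in SAP 3.8, to match Protocol 4.8.5.2 and SAP 3.7.1.
- In SAP 3.9, define ADA status as status up to and including the visit of the concentration.

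The cost is SAP wording, one table shell and one listing, all from dates already collected. The downside is small counts in each part of the split, so it should be read case by case.

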3.2.3 Rationale for Endpoints

MEDI8897 is being developed to provide RSV immunoprophylaxis for all infants entering their first RSV season and children with CLD of prematurity or hemodynamically significant CHD entering their first and second seasons. The primary endpoint for this study is safety and tolerability, with the aim of comparing the profiles for MEDI8897 and palivizumab in this population. The standard measures of TEAEs/TEAEs, AESIs, and NOCDs will be used for this assessment. All subjects will be followed for approximately 1 year after the last dose of MEDI8897. Subjects with CLD/CHD who receive MEDI8897 for Season 1 and Season 2 and subjects who receive a replacement dose of MEDI8897 after cardiopulmonary bypass will provide data for the safety assessment of infants who receive more than a single dose of MEDI8897.

Serum concentration of MEDI8897 at selected time points will be evaluated as a secondary endpoint to confirm that serum concentrations are maintained at an efficacious level for at least 5 months after dosing. Palivizumab serum concentrations will also be evaluated. MEDI8897 and palivizumab PK data will be summarized by non-compartmental analysis. Additionally, serum concentration data will be used to characterize the PK of MEDI8897 in infants using a population PK approach separately. For infants who require hospitalization for

LRTI or any respiratory infection, an additional serum sample for measurement of MEDI8897/palivizumab concentration and ADA will be obtained contemporaneous with time of hospitalization. Exposure-response analysis will be performed to relate MEDI8897 serum concentrations and efficacy endpoints (LRTI including RSV-associated hospitalization).

To determine MEDI8897 and palivizumab serum levels post dosing and to correlate with the potential development of ADA, serum concentrations will be measured up to 360 days post Dose 1 (when MEDI8897 would be given) for both Season 1 and, as applicable, Season 2. ADA to MEDI8897 and to palivizumab will be measured at selected time points throughout the study and up to 360 days post Dose 1 for each season as well.

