ADA = anti-drug antibody; AEs = adverse events; AESIs = adverse events of special interest; CHD = congenital heart disease; CLD = chronic lung disease; D = study day; ER = emergency room; HRU = healthcare resource utilization; ICU = intensive care unit; IM=intramuscular; LRTI = lower respiratory tract infection; neut Ab = neutralizing antibody; NOCDs = new onset chronic diseases; OTC = over-the-counter; PK = pharmacokinetic; Q2W = once every 2 weeks; RSV = respiratory syncytial virus; SAEs = serious adverse events; SID = subject identification; TC = telephone call; V = visit.

^a Visit 2/Day 1 and Visit 1/Screening can occur on the same day.

^b For subjects in the CLD/CHD cohort, the Season 1 Visit 9/Day 361 may be the same as the Season 2 Visit 10/Day 1 (Dose 1).

^c All vital signs (temperature, blood pressure, heart rate, and respiratory rate) should be obtained within 60 minutes prior to dosing, and at 30 minutes (± 5 minutes) and 60 minutes (± 5 minutes) post dose.

^d Subjects requiring a replacement dose of study drug due to cardiac surgery with cardiopulmonary bypass will have a blood sample collected before and after surgery (prior to administering replacement dose) for PK evaluation.

^e If Visit 1/Screening and Visit 2/Day 1 do not occur on the same day, blood sample for PK, ADA, RSV neut Ab, and RSV serology can be collected at either Visit 1/Screening or Visit 2/Day 1 predose.

^f Nasal samples will be collected from all subjects with LRTIs (inpatient or outpatient) and from all hospitalized subjects with any new respiratory infection (upper or lower) within approximately 2 days after the initial healthcare provider assessment and diagnosis.

Blood samples will be collected from all subjects hospitalized with LRTI or any respiratory infection within approximately 2 days following hospital admission.

^g Subjects in each cohort (preterm and CLD/CHD cohorts) will be randomized 2:1 to receive either MEDI8897 administered as a stratified dose by weight band, which includes a single fixed 50-mg IM dose for infants weighing < 5 kg or 100-mg IM dose for infants weighing ≥ 5 kg, followed by 4 once-monthly IM doses of placebo; or 5 once-monthly IM doses of 15 mg/kg palivizumab.

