- If there are 2 or more valid, non-missing observations within the same visit window, and
 - if they are on different days, then the non-missing one which is closest to the scheduled visit day will be used in the analysis.
 - if they are on the same day which is closest to the scheduled visit day, then the non-missing one with the later collection time will be used in the analysis.
- If 2 or more valid observations are equidistant from the scheduled visit, and
 - if they are on different days, then the non-missing observation with the earlier collection date will be used in the analysis for the post-baseline observations, and the non-missing observation with the later collection date will be used in the analysis for the screening observations.
 - if they are on the same day, then the non-missing observation with the later collection time will be used in the analysis.
- For LRTI visits or unscheduled visits, if 2 or more valid observations are collected on the same day, then the non-missing observation with the earlier collection time will be included in the analysis.
- If a visit window does not contain any observations, then the data will remain missing.
- For the visit-based summaries for ADA, if both ADA positive and negative samples are available within a subject's visit, ADA positive will be reported.

For assignment of data to adjusted analysis-defined visit windows, study day will be defined as:

- Screening period: Study day = Date of assessment date of randomization
- After randomization: Study day = Date of assessment date of randomization + 1

The adjusted analysis-defined windows for ADA, RSV neutralizing antibody, and RSV serology are defined in Appendix 2, and for clinical laboratory data are defined in Appendix 3.

The partial dates imputation rules are described in Appendix 4 and Appendix 5.

Categorical data will be summarized by the number and percentage of subjects in each category. Continuous variables will be summarized by mean, median, standard deviation, minimum, and maximum. In general, unless stated otherwise, baseline of each season will be defined as the last non-missing value within 30 days prior to the 1st dosing of the season. Baseline of Season 1 + Season 2 will be the same as baseline of Season 1.Data analyses will be conducted using the SAS® System Version 9.4 or higher (SAS Institute Inc., Cary, NC).

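### ADA status in the efficacy and safety impact tables counts any positive sample, and a respiratory hospitalization adds a sample, so classification leans toward the outcome; the bias is within arm and small

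*SAP*

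**What the plan says.** SAP 3.8 sets out to assess the impact of ADA on efficacy and safety. It splits infants by post-baseline status, "at least one post-baseline ADA positive or not through 360 days post 1st dose", and tabulates medically attended RSV LRTI, RSV hospitalization, TEAEs and SAEs in each group. It adds a shorter window: "The efficacy endpoints will also be summarized by ADA post-baseline status through 150 days post 1st dose". Neither definition is confined to scheduled visits.

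The scheduled PK and ADA draws are common to all infants. The Figure 1 notes in Protocol 3.1.1 give them for Season 1 as "Screening or Day 1 predose and on Days 31 (predose), 151, and 361". SAP Appendix 2 shows no Day 31 window for the EU version, which leaves Days 151 and 361 there.

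A further draw depends on illness. The same notes continue: "Additionally, samples will be collected during both seasons from all subjects hospitalized for a respiratory infection". Protocol 3.2.3 confirms that it is tested for ADA: "an additional serum sample for measurement of MEDI8897/palivizumab concentration and ADA will be obtained contemporaneous with time of hospitalization". The footnotes to Tables 5 and 6 in Protocol 4.2.2 fix the timing: "Blood samples will be collected from all subjects hospitalized with LRTI or any respiratory infection within approximately 2 days following hospital admission". For an outpatient LRTI, Protocol 4.3.1.1 asks for respiratory secretions and no blood.

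SAP 3.1 allocates every observation to a visit window and has a rule for choosing among same-day observations at LRTI visits. No text in either document removes the triggered samples from ADA status.

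**The concern.** Under an ever-positive rule, one more test can leave the chance of being called positive unchanged or raise it, but cannot lower it. SAP 3.8 itself defines transient positivity, so an admission sample can be an infant's only positive. The infants who get this additional test are those with the outcome being tabulated: an RSV hospitalization, or an SAE that is a respiratory hospitalization. ADA status therefore depends partly on the outcome. The 150-day version does not remove this, because an admission sample taken within that window still counts.

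At stake is the reading of the tables meant to show whether ADA reduces protection or harms safety. An excess of RSV hospitalizations or respiratory SAEs among ADA-positive infants could come from unequal sampling alone, and with few ADA-positive infants a reader could not tell the two apart.

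**Working it through.** **Inputs**
- Post-baseline ADA in the Phase 2b MEDI8897 group: 40/921 (Protocol 1.4.1). Check: 40/921 = 4.34%, stated as 4.3%.
- Assumed RSV hospitalization 1.9% and outpatient RSV illness 3.9% (Protocol 4.8.2). Their sum is 5.8%, stated as 6%.
- MEDI8897 infants in Season 1: 600.
- Phase 2b MEDI8897 TESAEs: bronchiolitis 2.1%, LRTI 1.4%, pneumonia 1.4%, bronchitis 1.2% (Protocol 1.4.1).

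**Assumptions**
- ADA has no true relation to outcome.
- The scheduled draws alone give P = 4.34% ever-positive. The protocol does not give the Phase 2b sampling schedule, so this is a working value.
- The extra draw has the same per-draw positivity q as a scheduled draw.

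**Chance of being classed positive**

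With k scheduled draws, q = 1 − (1 − P)^(1/k). If the extra draw is independent of the others, the chance becomes P + (1 − P)q. If it is wholly redundant, the chance stays at P.
- k = 3 (Days 31, 151, 361): q = 1.47%; 4.34% + 95.66% × 1.47% = 5.75%; ratio 5.75/4.34 = 1.32.
- k = 2 (through 150 days, or the EU schedule through 360 days): q = 2.20%; 4.34% + 95.66% × 2.20% = 6.44%; ratio 1.48.
- If the draw carries half of the independent information, the ratios are 1.16 and 1.24.

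The range is therefore 1.00 to 1.32 for three scheduled draws and 1.00 to 1.48 for two. The EU case also assumes that EU sites take the hospitalization sample.

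**RSV hospitalization row, k = 3, independent draws**
- Hospitalized infants: 600 × 1.9% = 11.4.
- Extra ADA-positive infants: 11.4 × (5.75% − 4.34%) = 0.16.
- ADA-positive group: about 600 × 4.34% = 26.
- Apparent hospitalization rate: 2.50% in ADA-positive against 1.87% in ADA-negative infants, a ratio of 1.33 from sampling alone.

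**Respiratory SAEs, k = 3, independent draws**
- Ignoring overlap, and taking all these events as hospitalized and the Phase 2b rates as applicable: 2.1 + 1.4 + 1.4 + 1.2 = 6.1%, or 36.6 of 600.
- Extra ADA-positive infants: 36.6 × 1.41% = about 0.5.

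**RSV LRTI row**
- The share of cases that trigger blood is 1.9/5.8 = 33%.
- The ratio falls to at most 1 + 0.33 × 0.32 = 1.11 (k = 3), and to at most 1.16 (k = 2).

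**Leverage of one infant:** 1/26 = 3.8 percentage points, against an assumed RSV hospitalization rate of 1.9%.

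**The case against.** The strongest objection is size. The excess is a fraction of one infant, and the ratios at the top of each range require independent draws, although ADA can persist. With 11.4 RSV hospitalizations expected, the chance that none falls in the ADA-positive group is about 60% without the bias (0.9566^11.4) and about 51% at its upper end (0.9425^11.4). Protocol 4.8.2 adds that event rates could be much lower. A reader might infer that the table will show more RSV hospitalizations among ADA-positive infants. The documents do not support that: the direction of the bias follows from the design, but an empty cell is the likeliest result either way.

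Two other stronger readings also fail. SAP 3.1 says that "if both ADA positive and negative samples are available within a subject's visit, ADA positive will be reported", and it is tempting to see this as the source of the problem. That rule is confined to visit-based summaries. The impact tables use a subject-level status in which one positive suffices without any override. Nor does the SAP say that infants with no post-baseline sample count as ADA-negative. It gives no denominator for these tables, and the Phase 2b rates used only infants with samples available.

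The remedy can be disputed too. The admission sample is taken specifically to measure ADA at hospitalization, so a status that ignores it would class an infant with confirmed ADA at breakthrough as negative. That stands, and it is a reason to keep the ever-positive table alongside. It is also true that Day 151 and Day 361 results drawn after an event would still define status. A scheduled-only rule equalizes the planned sampling but does not put ADA before the outcome.

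These points limit how much the issue matters. They do not change the fact that, under the written rule, infants with the outcome are sampled more often.

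**Conclusion.** The point holds as a modest within-arm bias. Read as written, SAP 3.8 lets a sample triggered by the outcome help to define the group in which that outcome is counted. The effect applies fully to RSV hospitalization and to SAEs that are respiratory hospitalizations. It applies only in part to RSV LRTI, and to few TEAEs. It does not touch the randomized comparison, since both arms are sampled alike, and no hypothesis is tested.

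The sizes above rest on the Phase 2b rate carrying over to this population, on that rate arising from scheduled draws alone, and on an extra draw somewhere between redundant and independent. Missed scheduled samples could shift them either way. What makes the point worth acting on is the small ADA-positive group, where a single infant classed positive only because of an admission sample would visibly change the rate.

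**What to change.** In SAP 3.8, present the efficacy and safety impact tables with ADA status based on scheduled samples only (Days 31, 151 and 361, as applicable). At minimum, provide this as a sensitivity table beside the ever-positive version. State that hospitalization-triggered ADA results are listed separately. Use infants with at least one scheduled post-baseline ADA result as the denominator, which also settles how infants without a sample are handled.

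The cost is one or two sentences, a scheduled/triggered flag in the ADA dataset, and a repeat of a few tables. The downside is that a positive seen only at a triggered draw is listed rather than counted in the scheduled-only table; keeping the ever-positive table means that it is not lost.
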